After the 3 month visit, all patients will continue to be followed and a health history questionnaire will be completed at 6 months and one year.

3. General Patient Management Guidelines and Other Therapy

For all patients:

- a. Admission to a Neurology Special Care area or Intensive Care Unit.
- b. Therapy for acute stroke other than rt-PA (including heparin or antiplatelet drugs) will not be initiated during the infusion or for 24 hours following the onset of symptoms (see C.4).
- c. Supplemental oxygen as indicated.
- d. Initially NPO; later, diet as tolerated and no nasogastric tube (NGT) for at least 24 hours except when clinically indicated and no other less invasive option is available.
- e. IV fluids to maintain adequate urine output during the first 24 hours.
- f. Cardiac Monitoring.
- g. Blood pressure monitoring and appropriate measures to control BP within acceptable limits.
- h. Central venous pressures, pulmonary artery pressure, and cardiac output monitored as indicated but not prior to, during the 60 minute rt-PA infusion,

or for 30 minutes following the end of rt-PA infusion unless an emergency situation intervenes. Pre-existing peripheral lines may be maintained but will be closely watched and compressed if removed.

- i. As already noted, uncontrolled hypertension would pose a potentially serious risk of bleeding to these patients; but, rather than continuously monitoring blood pressure with an arterial cannula, which would pose its own set of risks, we prefer to rely on frequent (every 15 minute) blood pressure monitoring during the first two hours and every 30 minute monitoring for 6 hours thereafter before relaxing the monitoring to every 60 minutes for the next 16 hours.
- j. Neurological check by evaluation of level of consciousness and weakness in the arms and legs performed every 15 minutes for the first 2 hours, every 30 minutes for the next 6 hours, and hourly thereafter for the next 16 hours (using methods for motor arm and leg described in the NIH Stroke Scale).
- k. Urinalysis (results to be reported when obtained for medical indications). Urinary catheterization shall be avoided if possible, especially until 30 minutes following completion of rt-PA treatment.
- l. Stool guaiac and NGT guaiac (results to be reported when obtained for medical indications).
- m. The patient will be under the immediate supervision of one of the named trial investigators until after the 2 hour post treatment exam is completed.
- n. If the patient is admitted to the emergency department, the goal will be to begin treatment within 55 minutes from the time of admission. If the patient is hospitalized at the time of stroke onset, the goal is to begin treatment within 55 minutes of the time of notification of a trial investigator. In other words, the only acceptable delays are those which delay the arrival of the patient to the hospital.
- o. Physical, occupational and speech therapy should be started as soon as possible when appropriate.

If, during or after infusion, sudden worsening occurs in any patient, (a) a neurological evaluation will be performed and reported, (b) a CT scan will be done as soon as possible, and, (c) if hemorrhage is discovered, the Coordinating Center will be notified within two hours. If worsening occurs after infusion, clinical management will proceed at the discretion of the investigator.

4. Adjunctive Stroke Therapy

Although heparin and to a lesser extent aspirin are conventionally used in patients with coronary thrombosis to prevent re-occlusion and maintain arterial patency after

rt-PA therapy, no adjunctive antithrombotic therapy will be given in this trial during the first 24 hours after the onset of symptoms, until after the patient has had their 24 hour exam and the CT scan has been evaluated. At that time, standard medical therapy can be given. Standard medical therapy may include aspirin (325-1300 mg daily), or heparin (for example mini-dose for prevention of deep vein thrombosis or full dose for prevention of recurrent cerebral embolism). If full dose heparin is used, the 24 hour CT scan should be reviewed and if clinically indicated a new CT scan obtained to exclude cerebral hemorrhage. No heparin bolus should be given, and the PTT should be maintained no more than 2 x control. If full dose of heparin is used, the PTT should be monitored daily and platelet count every other day, and these results recorded on the case report form. A form will be completed documenting any aspirin or other antithrombotic therapy used by any patients during the two weeks prior to entry in the trial. IV crystalloid therapy should be given to maintain euvolemia, but hypervolemic therapy with either colloid or blood substitutes should not be used. Standard antihypertensive therapy may be used as needed. If calcium channel blockers are used, their use should be carefully recorded. Osmotic agents such as mannitol or glycerol, intubation with hyperventilation, muscular paralysis, and sedation can be used in the setting of uncontrolled elevation of intracranial pressure. Corticosteroids should be avoided unless specifically indicated for a systemic condition. Central nervous system active drugs such as sedatives and hypnotics should be avoided. Antidepressant drugs can be given if clinically indicated.

These limitations on adjunctive therapy will minimize any risk of cerebral hemorrhage associated with combined rt-PA and antithrombotic therapy. They will also prevent the introduction of a second form of therapy which would confound the interpretation of data.

5. Management of Hemorrhage

If the worsening occurs during the infusion and intracerebral hemorrhage is suspected, the rt-PA infusion will be discontinued. Each center will be responsible for having personnel trained and available at all times to treat intracerebral hemorrhage in patients receiving rt-PA. A suggested management plan approved by the Steering Committee is given in the Manual of Procedures.

6. Mortality and Adverse Effects

Although mortality is not an outcome for this trial, mortality will be evaluated. The Clinical Center will call the Coordinating Center within two hours after a patient's death is ascertained. Calls will be monitored regularly by Coordinating Center staff to insure

notification of the FDA within the required time frame. The Clinical Center will obtain the death certificate and other documentation (information from witnesses, relatives, autopsy information, hospital or physicians records, if possible), and complete the relevant study forms. This documentation should be forwarded to the Coordinating Center. All names should be removed and a study I.D. should be written on each document. Deaths will be coded by a nosologist retained by the Coordinating Center using the death certificates and other relevant medical information. Should there be a need for a more detailed review in the future, the information will be available in the patient's file. Data on mortality will be provided to the Safety and Data Monitoring Committee and to the FDA.

A similar procedure should be followed for any life threatening/serious adverse effects (see manual of procedures for definition). The Coordinating Center should be called within 2 hours of the Clinical Center's notification that a life threatening adverse effect occurred. For any other adverse effects, an adverse experience form should be completed and forwarded to the Coordinating Center as soon as possible. The Coordinating Center will notify Genentech within 72 hours of any adverse event or death reported to the FDA.

V. Conduct Of The Trial

A. Training and Orientation

Initial training and information meetings will be held for patient coordinators, clinical coordinators, neurologists, laboratory staff and neuroradiologists from each clinical center prior to the start of data collection for the trial.

B. Patient Safety and Confidentiality

Patients participating in a clinical trial have the right to privacy. Thus, stringent policies relating to confidentiality will be adopted for this trial. Name, social security numbers or medical record numbers will not be included on forms sent to the Coordinating Center. A stringent password protection program is in effect for the data files. Additionally, any forms collected for the study will be stored in locked file cabinets. As further protection study staff will sign a confidentiality policy.

On monitoring visits Coordinating Center staff will need to review some patient charts. However, no names or medical record numbers will be recorded on any

monitoring visit reports. Coordinating Center staff will be bound by the same confidentiality policies as noted previously.

With regard to patient safety, interim analyses will be carried out prior to Safety and Data Monitoring Committee meetings. Tabulations of all side effects, by treatment group, will be prepared and presented to the Data and Safety Monitoring Committee as requested.

C. Data Monitoring and Quality Control

Once a year a team from the Coordinating Center will visit each clinical center to monitor clinical performance. At some centers, the Coordinating Center team may need to visit more frequently. Additionally a clinical research nurse (CRN) will make frequent unscheduled visits to the centers to review and compare case report forms and medical records.

The Study Coordinator at each clinical center has responsibility for all data collected in that center. Information gathering is standardized at the clinical centers through the manual of procedures and training mentioned previously.

At the Coordinating Center quality assurance procedures will be carried out for data entry, data coding, laboratory analysis and CT readings.

D. Data Analysis

For each time group (≤ 90 , > 90 to ≤ 180 minutes from stroke onset) and for the two time groups combined, the primary outcome variable is defined as an improvement from admission of four points in the Stroke Scale within 24 hours from stroke onset or complete resolution of the neurological deficit. Separate Mantel-Haenszel analyses will be used to test for a treatment effect within a time group. Clinical centers will be the strata. A Mantel-Haenszel analysis will also be used to test for a treatment effect in the two time interval groups combined. In this analysis strata include clinical center and time from onset of symptoms (≤ 90 , > 90 minutes). Interim analyses for the primary endpoint will be carried out every 6 months just prior to each Safety and Data Monitoring Committee meeting with adjustment of critical levels as appropriate using methods of Fleming and O'Brien (21). Symmetric boundaries will be used.

Although this is a Phase II trial with an intermediate endpoint, status at 24 hours post treatment, the secondary endpoint, status at 3 to 6 months is also of interest. An opportunity would be lost to gather longer term clinical information on outcome at three

to six months if the trial was terminated early based on efficacy at 24 hours. For this reason, median standardized NIH Stroke Scale change score at 3 months, also will be included in the interim analyses every 6 months. The test statistic will be based on a stratified nonparametric analysis. Any decision to stop the trial based on efficacy would require consideration of both the primary endpoint at 24 hours and secondary endpoint at 3 months and would not be based solely on statistical considerations. A decision to stop for efficacy would take into consideration the potential for gathering further data on toxicity and on the natural history of the placebo group. This decision would also be balanced by consideration of the effect of withholding treatment from future stroke patients.

Multivariate analyses will be carried out as appropriate. Interim analyses will also be carried out for hemorrhage and mortality. Mantel-Haenszel and logrank tests will be used. For these analyses the upper boundary will be developed using the method of Fleming and O'Brien. The lower boundary will be set arbitrarily at -2.0 as suggested by DeMets and Ware (22-23). This will allow stopping of the trial if a strong, albeit non-significant trend in an adverse direction is observed. Because of safety concerns, the interim analyses of adverse events will be performed on a schedule related to the number of events. After every three symptomatic hemorrhagic conversions or hematomas an interim analysis will be done. The number three is based on the data from the previous pilot study (Background) study. Also, after every ten deaths there will be an interim analysis.

Because this is a Phase IIB trial, numerous secondary hypotheses and subgroup analyses have also been proposed.

E. Authorship of Papers

As previously agreed any publications or presentations of data on trial patients must have the permission of the NINDS. Also centers are not to separately present or publish data relating to the objectives of the trial. The NINDS t-PA Stroke Trial Group will be listed as author on major trial publications. Investigators, the NINDS project officer, and committees will be listed at the end of the paper.

VI. Organizational Structure

A. Introduction

The participating units in this collaborative clinical trial include: nine individual clinical centers, a Coordinating Center which includes a laboratory and CT scan reading center, the NINDS Division of Stroke and Trauma.

B. Participating Sites

1. Clinical Centers

Nine clinical centers will be responsible for recruiting the required number of patients, administering the study drugs, coordinating patient care, and collecting the information required by the trial protocol. The Principal Investigator is responsible for the overall conduct and performance of the clinical center. The organization of each clinical center will differ, but each clinical center will have one person specifically identified as the clinical coordinator and one person identified as the patient recruitment coordinator. The clinical coordinator will be responsible for such critical matters as checking Emergency Room logs, appointment scheduling, checking the completeness of forms, and arranging the shipment of blood specimens and CT data to the Coordinating Center.

2. Coordinating Center

The Coordinating Center will provide overall guidance and coordination of the data management, quality control, data analysis for the study, centralized measurement of fibrin and fibrin-fibrinogen degradation products and monitoring for safety. This will include preparation of the procedure manual, data collection forms and the various reports. Although the primary responsibility for early recruitment is at the clinical centers, the Coordinating Center will assist in this effort, not only by monitoring the degree of success at the various centers, but also by holding meetings of the patient recruitment coordinators to develop recruitment strategies for each of the clinical centers and then monitoring the success of the implementation of these plans.

a. Coagulation Laboratory

Frozen plasma and serum will be sent from the clinical centers to the Coordinating Center coagulation laboratory. The coagulation laboratory at Henry Ford Hospital will

receive and analyze frozen plasma samples for fibrinogen and frozen serum for the fibrinogen degradation products.

b. CT Reading Center

The clinical centers will send CT scan data to the Coordinating Center for reading. Although centers will have read the baseline scan to determine eligibility, these scans should also be sent to the Coordinating Center to be read. All clinical center sites will be asked to send data tapes and hard copies of each CT of the brain.

The initial interpretation will include:

- A description of the quality of the study
- Presence or absence of an infarct
- The arterial or venous distribution of the infarct.
- The infarct and brain volume.
- Any additional findings on the CT scan that can affect the management of the patient.
- The presence or absence of hemorrhage

3. The NINDS Division of Stroke and Trauma

The NINDS provides research funding for the trial, monitors the trial with respect to safety, monitors performance, and gives scientific direction to the trial.

C. Study Administration

1. Steering Committee

The Steering Committee includes principal investigators from each clinical center, the NINDS Project Officer and the Coordinating Center principal investigator and co-principal investigator. The Steering Committee will prepare the final protocol and provide scientific direction for the study at the operational level. The Steering Committee will advise and assist the Coordinating Center on operational matters, monitor the performance of the clinical centers and receive requests for any proposed ancillary studies. The Steering Committee will also report major problems and recommend changes in the protocol to the Project Officer and the Safety and Data Monitoring Committee. Beyond providing study guidance, the Steering Committee also provides the forum for Principal Investigators to serve as study collaborators.

2. Executive Committee

The Executive Committee consists of the Coordinating Center Principal Investigator and Co-principal Investigator and the Project Officer. The Executive Committee of the Steering Committee will review all unblindings. Where the decision to unblind is not related to an emergency situation, the clinical investigator should discuss the need to unblind with the Executive Committee prior to unblinding.

3. Sub-committees

Planning Committees

During the planning stages of the trial subcommittees will be formed to provide input in areas specific to the protocol or patient management.

The Steering Committee will appoint the following subcommittees:

The **Publications Subcommittee** will establish a procedure for reviewing every scientific paper or abstract using unpublished t-PA trial data (including ancillary study data) prior to forwarding the paper for approval by the NINDS. This subcommittee will also review every paper using published t-PA trial data which purports to represent official t-PA trial views or policy. This policy applies to papers prepared for publication or oral presentation. The subcommittee will also review ancillary studies to ensure patient safety, trial design and scientific integrity are not compromised prior to submitting the study to the Steering Committee for review and the NINDS for approval.

The **Quality Assurance Subcommittee** will monitor the performance of the clinical centers, Coordinating Center, central laboratory and CT reading center. Outcome data is not reviewed by this subcommittee. The NINDS will appoint an independent board to monitor all aspects of the trial.

The **Stroke Scale Subcommittee** will address issues relating to the reliability, validity, and redundancy in the NIH Stroke Scale and other measures of neurologic function. The subcommittee will also develop definitions for the manual of procedures and address procedural questions relating to the scales throughout the trial.

4. Safety and Data Monitoring Committee

The Safety and Data Monitoring Committee will act in an advisory capacity to the NINDS on policy matters throughout the trial. This group also periodically reviews trial

results and reports of adverse effects. The Board is selected by the NINDS and is comprised of members who are not trial investigators. Board meetings are attended, when appropriate, by senior investigators from the Coordinating Center including the principal investigator, co-investigator and other Coordinating Center investigators as necessary. The Board will review the final protocol, review any subsequent changes to the protocol including any necessary changes to the dose schedule, and make recommendations on early termination of the trial (if appropriate). The Board will also review clinical center performance, make recommendations and assist in resolution of problems reported by the Steering Committee.

5. Clinical Coordinators' Committee

The Clinical Coordinator's Committee will discuss issues relevant to patient management and data reporting. This committee is composed of all the clinical coordinators from the clinical centers and the clinical coordinator from the Coordinating Center.

6. Patient Coordinators' Committee

The Patient Coordinators' Committee will discuss issues relevant to community education and patient recruitment. This committee is composed of all the patient recruitment coordinators from the clinical centers and the coordinator and health educators from the Coordinating Center.

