Since completion of the initial study, 18 additional patients have been treated at a dose of 32 or 37 mg/meter² without subsequent hemorrhage (unpublished data). In addition, 20 patients were subsequently treated at 91-180 minutes from symptom onset ([name]: Written communication July 30, 1990). Of the 20 patients, four had at least a four-point improvement on the NIH Stroke Scale Score at 24 hours. There were two intracerebral hemorrhages, one at a dose of 32 mg/meter² and another at 37 mg/meter² respectively. The proposed dose of rt-PA for the present study, 0.9 mg/kg, is roughly equivalent to the dose tier 32 mg/meter² in the pilot study. At this dose, 13 (48%) of 27 patients treated within 180 minutes had at least a four-point improvement on the NIH Stroke Scale Score at 24 hours and one developed an intracerebral hemorrhage.

Preliminary interim results of another dose-escalation safety study of rt-PA for acute cerebral infarction have been reported in abstract form (20). Patients who had an acute cerebral infarction and angiographic documentation of an appropriate arterial occlusion were treated with a 60-minute infusion of rt-PA within eight hours of symptom onset. Upper dose levels exceeded the highest dose tiers of the NINDS pilot study. The primary positive efficacy response was angiographically documented reperfusion of the previous occlusion. The primary negative safety response was intracerebral hematoma. Of the first 57 patients, 22 (39%) patients had complete or partial arterial recanalization at 60 minutes. Intracerebral hematoma occurred in four patients, three of which were fatal. Data concerning neurologic outcome have not yet been reported.

The NINDS pilot study indicates that ischemic stroke patients can be treated with intravenous rt-PA within 90 minutes of symptom-onset with relative safety and with

significant early neurologic improvement in over 40%. Data on patients treated from 91-180 minutes from symptom onset are more limited. However, because of the lack of controls, either randomized or historical, convincing evidence of any effect attributable to rt-PA is lacking. Therefore, before a larger trial to test efficacy can be justified, a smaller Phase II-B study with controls must be completed.

III. Objectives

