 - a. and treated with rt-PA will be more likely to show improvement at 24 hours from onset of stroke than patients treated with rt-PA with no previous usage of ASA due to ASA's effect on platelets and reocclusion problems;
 - b. will have a higher rate of symptomatic intracranial bleeding defined as either hemorrhagic conversion of cerebral infarction, or intracerebral hematoma in the area of the brain separate from the infarct, or subarachnoid hemorrhage, or subdural hematoma.

4. Patients who have a greater activation of the fibrinolytic system, as evidenced by a lower fibrinogen and higher FDP level will have a greater risk of symptomatic intracerebral hemorrhage as defined in 3b above.

IV. Design

A. Introduction

The target population for the t-PA trial includes men and women aged 18 and older admitted to a hospital emergency room with a confirmed ischemic stroke and able to begin treatment within 180 minutes of onset of symptoms. Every effort will be made to include women and minorities in the trial. Also included in the target population are patients in the same age group who have a stroke while already hospitalized. Patients who have contraindications to the use of rt-PA or other conditions thought likely to impair follow-up to three months will not be eligible for the study.

After completion of baseline examination, required laboratory tests, CT scan, informed consent, and randomization, rt-PA treatment will be initiated in eligible patients. Patients will be followed for one year.

Specifications for the estimation of sample size for the study are given in Appendix A. In general, the estimate of 140 patients for each time group is based on several assumptions: the expected percent of patients showing improvement based on the pilot trial (40%), low mortality in the first 24 hours, a two-tailed critical level of 0.05 and power of 0.95.

B. Enrollment

1. Recruitment

All centers will have a recruitment coordinator who will be responsible for enhancing efforts to recruit stroke patients soon after onset of symptoms. This person will be responsible for coordinating education of local communities and physicians. The goal of the educators program will be to encourage early presentation to the emergency department following the onset of stroke. There will also be education of prehospital care providers about the nature of the t-PA trial and their role in providing early assessment and transport.

2. Eligibility Assessment

a. Patient Log

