Appendix

Sample Size

Power estimates for the analysis are based on a two-sample test of proportions. Based on the pilot study at least 40% of the rt-PA group will show a 4 point decrease in the NIH Stroke Scale score or complete resolution of neurological deficit at 24 hours from onset of stroke. For the overall comparison of the two time groups combined there will be a sample size of 280 (140 per group). With 280, setting the critical level at 0.05, two-sided test, and absolute difference of 20% from control can be detected with a power of 0.95. (40% in rt-PA group versus 20% in controls). Within a time group (≤ 90 minutes or > 90 to ≤ 180 minutes) with a sample size of 140 (70 per group), setting the critical level at 0.05, two-sided test, an absolute difference of 24% from control can be detected with a power of 0.90. (40% in rt-PA group versus 16% in controls). Because of the risk of hemorrhage, the difference between rt-PA treated and placebo groups must be large to be clinically meaningful.

Calculations were based on the arc sine approximation to the binomial. Using a stratified analysis may slightly reduce the power of the analyses. The critical level for testing was not adjusted for multiple comparisons as each analysis is considered to be a separate experiment addressing a prespecified hypothesis.

The NINDS t-PA STROKE TRIAL PROTOCOL - PART B

I. Introductory Summary

Initially the trial was designed to address only short term outcomes. However, because recruitment progressed so rapidly for Part A it appeared to be possible to extend recruitment and address three month outcome as a primary hypothesis. At the time the decision was made there had been no formal analysis of the three month outcome data and the clinical investigators had not seen any data related to the estimated treatment effect. The protocols for Parts A and B are the same except for the objectives, background and data analysis plan. There were 290 patients in Part A and there will be 320 in Part B for a total of 610 in the entire Trial.

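### Part A's design section attaches power 0.95 to 140 patients per time group; its appendix gives 0.90 for that number, and only for a 24-point difference

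*Supplement*

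**What the plan says.** Part A, IV.A (Design, Introduction) sends the reader to the appendix for the specifications and then summarises them: "the estimate of 140 patients for each time group is based on several assumptions". The assumptions listed are a 40% improvement rate taken from the pilot, low early mortality, and "a two-tailed critical level of 0.05 and power of 0.95". No control rate or difference is given there.

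The Part A appendix (Sample Size) makes two statements:

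- **Both time groups combined:** 280 patients, 140 per arm, 40% versus 20%, two-sided 0.05, power 0.95.
- **Within a time group:** for 140 patients, 70 in each arm, and the same two-sided level, the appendix states that "an absolute difference of 24% from control can be detected with a power of 0.90". The rates behind this are 16% for control and 40% for rt-PA.

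The appendix names the arcsine approximation as its method. It takes the treated response from the pilot: "Based on the pilot study at least 40% of the rt-PA group will show a 4 point decrease". It uses that 40% for the combined comparison and within each time group.

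The Part A Background gives the pilot results at 24 hours. Within 90 minutes, 34 of 74 (46%) improved by at least four points. For 91-180 minutes: "Of the 20 patients, four had at least a four-point improvement on the NIH Stroke Scale Score at 24 hours". At roughly the dose chosen for the trial, 13 of 27 (48%) treated within 180 minutes improved.

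**The concern.** IV.A and the appendix give different powers for the same number of patients at the same significance level. In the appendix, 140 is both the number per arm in the combined comparison and the number of patients in one time group. The 0.95 that belongs to the first appears to have been attached to the second. That is an inference, but it fits the figures.

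The difference matters because each time group is a primary hypothesis in its own right (Part A, III.A, hypotheses 1 and 2), and the appendix treats each analysis as a separate experiment. Suppose the 91-180 minute result is not significant. A reader who holds the 0.95 from IV.A would take it as stronger evidence against a late benefit than the appendix allows.

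The response assumption adds to this for the late group. The same 40% is used in both strata, although the pilot's late patients did less well. Part A itself plans a sub-group test on the premise that response to rt-PA differs between the time groups (III.D, hypothesis 1).

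**Working it through.** **Method.** The appendix's arcsine approximation, with n per arm and a two-sided level of 0.05:

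power = Φ( |2·arcsin√p1 − 2·arcsin√p2| · √(n/2) − 1.96 )

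Transformed rates, 2·arcsin√p: 40% → 1.3694; 20% → 0.9273; 16% → 0.8230; 10% → 0.6435; 5% → 0.4510.

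**Step 1: reproduce the appendix.**

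- Combined, n = 140, 40% vs 20%: 0.4421 × √70 − 1.96 = 1.739, so power is 0.959 (stated 0.95).
- One time group, n = 70, 40% vs 16%: 0.5464 × √35 − 1.96 = 1.273, so power is 0.898 (stated 0.90).

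Both agree. A pooled-variance normal approximation gives 0.959 and 0.894.

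**Step 2: test the IV.A figure, 0.95 with 70 per arm.**

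- 40% vs 16% (24 points): 0.898, as above.
- 40% vs 20% (20 points): 0.4421 × √35 − 1.96 = 0.656, so power is 0.744.
- A one-sided test at 40% vs 16% would give 0.944, but both sections specify a two-sided test.

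Neither of the appendix's rate pairs gives 0.95.

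**Step 3: what 0.95 would require.**

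- With 70 per arm and 40% on rt-PA, the transformed difference must be (1.960 + 1.645)/√35 = 0.6093. The control rate is then sin²((1.3694 − 0.6093)/2) = 13.8%, a 26-point difference. The documents do not state this rate.
- With the appendix's rates, n per arm = 2 × (3.605/h)², where h is the transformed difference. This is 133 for 40% vs 20% (h = 0.4421) and 88 for 40% vs 16% (h = 0.5464).

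**Step 4: support for the 40%.**

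| Pilot patients | Improved | Rate | Exact 95% CI |
|---|---|---|---|
| 0-90 min | 34/74 | 46% | 34% to 58% |
| 91-180 min | 4/20 | 20% | 6% to 44% |
| These two pooled | 38/94 | 40% | 30% to 51% |
| About trial dose, within 180 min | 13/27 | 48% | 29% to 68% |

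The last two rows support 40% for the combined population. The time mix of the 27 is not given, so that row does not settle the late stratum.

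**Step 5: sensitivity for 91-180 minutes, 70 per arm, 20% on rt-PA.** The pilot had no controls, so the control rates here are assumptions.

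- Control 5%: 0.4763 × √35 − 1.96 = 0.858, power 0.80.
- Control 10%: 0.2838 × √35 − 1.96 = −0.281, power 0.39.
- Control 16%, the appendix's own rate: 0.1043 × √35 − 1.96 = −1.343, power 0.09. This is a 4-point difference, and the appendix says that only a large difference would be clinically meaningful.

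**The case against.** The strongest reply is that IV.A is only a summary. It refers to the appendix, opens its figures with a general qualifier and names no control rate, so it is not tied to either rate pair. The appendix is correct and openly states 0.90, 70 per arm and 24 points. Part A had also closed with 290 patients before the version of December 23, 1993, so no design decision now depends on the sentence. Much of this stands: the error is in a stated figure, not in the calculation behind the trial. It does not rescue the sentence, which names the time-group size, the significance level and the power together and still stands in the current text.

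On the 40%, the reply is stronger. The late-group 20% comes from 20 uncontrolled patients, at doses that included at least 32 and 37 mg/m², and its interval includes 40%. The pilot counted four-point improvement, whereas the trial endpoint also counts complete resolution, so 20% may understate the rate on the trial's endpoint. All of this stands. The 40% is unsupported for that stratum, not disproved.

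A reader might also infer that the combined comparison (primary hypothesis 3) lacks its stated power, because the trial balances early and late patients while the pilot did not. The documents do not support this. The 0.95 reproduces, and 13 of 27 at about the trial dose supports 40% or more within 180 minutes. A lower power would come only from reducing the treated rate while holding control at 20%, and nothing in the documents fixes control there.

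**Conclusion.** The power of 0.95 in IV.A is wrong as written for 140 patients per time group. On the appendix's figures it is 0.90 for a 24-point difference and 0.74 for a 20-point difference. The type II error is therefore about 10% or 26%, against the 5% implied. This rests on the appendix's own method, level and rates for an unstratified comparison; the appendix notes that stratifying may reduce power slightly.

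Separately, the 40% response has no specific support in the 91-180 minute group, where the only pilot figure is 4 of 20. The powers of 0.39 and 0.80 for that group are illustrations under assumed control rates, not estimates of the actual power.

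A reader might go further and treat primary hypothesis 2 as a matter of estimation only. The documents do not support that step. It is a prespecified primary hypothesis, and demoting it after Part A closed and its outcome data had been reviewed by the monitoring committee would be a substantive change, not a corrected figure.

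**What to change.** 1. **Part A, IV.A:** state power 0.95 for the combined 280 patients only (40% versus 20%). Within a time group of 140, state 0.90 for a 24-point difference (40% versus 16%) and 0.74 for 20 points (40% versus 20%).
2. **Part A appendix:** note that the 40% is supported for the combined population (38/94 pooled; 13/27 at about the trial dose within 180 minutes) but not specifically at 91-180 minutes (4/20, exact 95% CI 6% to 44%).
3. **Part A appendix:** add a sensitivity figure for the 91-180 minute group, with the control rates labelled as assumptions. For example, with 20% on rt-PA and 70 per arm, power is 0.39 against 10% and 0.80 against 5%.

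The cost is a few lines of text. No patients, analyses or hypotheses change, and the combined comparison keeps its stated power. The per-group power will read less favourably than IV.A now suggests.
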